13.5 Procedures for Handing Missing, Unused, and Spurious Data

All available efficacy and safety data will be included in data listings and tabulations. No imputation of values for missing data will be performed. The relevance of missing sample data will be assessed.

Data that are potentially spurious or erroneous will be examined according to standard data management operating procedures.

13.6 Demographic and Baseline Characteristics

Demographic and baseline characteristics will be summarized, including gender, age, race, weight, height, body surface area (BSA), primary diagnosis, and other parameters as appropriate. No inferential statistics will be carried out.

13.7 Data Analysis Plan

13.7.1 Primary Objective

Phase I portion: There is no primary efficacy endpoint for the dose escalation portion of the study. Toxicity data will be summarized and tabulated for all and for each dose level.

Phase II portion: The phase II is not intended to demonstrate differences in treatment outcomes among disease groups, although potentially informative data will be subjected to exploratory analysis. The primary endpoint is ORR. ORR is defined as the rate of CRs and PRs in the response-evaluable population. It will be estimated with 95% exact binomial confidence intervals (CIs), while considering the adaptive nature of Simon's two-stage design.

13.7.2 Secondary Objectives:

There is no secondary efficacy endpoint for the Phase I portion of the study.

Phase II study: the secondary efficacy endpoints for are ORR in FLT-3 mutant and FLT-3 WT populations, DOR, mortality rate at 3 and 6 months, and OS (by FLT-3 mutant cohort, FLT-3 WT cohort, and combined cohort). DOR is defined as the time from the date of first documentation of a response to the date of first documented progressive disease (TTP). OS is defined as the time from the date of study entry to death. ORR will be estimated with 95% exact binomial confidence intervals (Cis). Time-to-event data will be analyzed by the Kaplan-Meier method. OS at 3 and 6 months and by FLT-3 mutant cohort, FLT-3 WT cohort, and combined cohort) will be estimated using the Kaplan-Meier along with 95% CIs.

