1.4.5 Clinical Efficacy

In Study C34002, 26 patients were evaluable for response, with 6 patients achieving >90% FLT3 inhibition at Cycle 1 Day 15 (100 mg QD, n = 1; 120 mg QD, n = 1; 160 mg QD, n = 1; 80 mg BID, n = 3). An additional 7 patients achieved >90% FLT3 inhibition at a subsequent time point. Early signs of clinical activity were observed in both FLT3-mutated and FLT3-WT patients. Three patients achieved response per International Working Group criteria at higher TAK-659 dose levels: 1 CR (FLT3-WT/160 mg QD) and 2 CRs with incomplete hematologic recovery (FLT3-WT/140 mg QD; FLT3-ITD/160 mg QD). An additional 6 patients achieved >50% bone marrow blast reduction from baseline without bone marrow recovery (n = 2, FLT3-ITD/100 mg QD; n = 1, FLT3- tyrosine kinase domain/120 mg QD; n = 1, FLT3- tyrosine kinase domain/160 mg QD; n = 2, FLT3-ITD/80 mg BID). The FLT3-WT patient who achieved CR at Cycle 4 maintained the CR through Cycle 10 despite achieving a maximal FLT3 inhibition of only 47% (Cycle 1 Day 15), suggesting that SYK inhibition may have contributed to this patient's response (24).

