2.2 Endpoints

2.2.1 Primary Endpoint

Phase I: Maximum tolerated dose (MTD) and recommended Phase II dose (RP2D) for the combination of TAK-659 plus Ixazomib in relapsed or refractory AML

Phase II: Overall response rate (ORR) defined as CR, CRp, CRi, and PR per Revised Recommendations of the International Working Group (IWG) for Diagnosis, Standardization of Response Criteria, Treatment Outcomes, and Reporting Standards for Therapeutic Trials in Acute Myeloid Leukemia.

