8.2 Disease Assessment

Assessment of disease response will follow the criteria outlined in the Revised Recommendations of the International Working Group (IWG) for Diagnosis, Standardization of Response Criteria, Treatment Outcomes, and Reporting Standards for Therapeutic Trials in Acute Myeloid Leukemia. (35) Investigators are encouraged to consult the reference for more detailed explanation of response criteria.

CR, CRi/CRp, and PR are defined using the following criteria:

Morphologic CR:

- A CR designation requires that the patient achieve the morphologic leukemia-free state and have an ANC of more than 1,000/uL and platelets of > 100,000/uL.
- A morphologic leukemia-free state requires less than 5% blasts in an aspirate sample with marrow spicules and with a count of at least 200 nucleated cells.
- There should be no blasts with Auer rods.
- Hemoglobin concentration or hematocrit has no bearing on remission status, although the patient must be independent of transfusions.
- There should be no residual evidence of extramedullary leukemia.

Morphologic CRi, CRp:

After chemotherapy, some patients fulfill all of the criteria for CR except for residual neutropenia (<1,000/uL) or thrombocytopenia (<100,000/uL).

PR:

- This designation requires all of the hematologic values for a CR but with a decrease of at least 50% in the percentage of blasts to 5% to 25% in the bone marrow aspirate. Thus, if the pretreatment bone marrow blast percentage was 50% to 100%, the percentage of blasts must decrease to a value between 5% to 25%; if the pretreatment blast percentage was 20% to less than 49%, they must decrease by at least half to a value of more than 5%.
- A repeat bone marrow aspiration after several weeks may be required to distinguish between a PR and increased blasts caused by bone marrow regeneration.
- A value of < 5% blasts may also be considered a PR if Auer rods are present.

Progressive Disease:

Because the IWG criteria for AML do not provide a standardized definition for progressive disease, in this protocol, progressive disease is defined as 1 of the following:

- >50% increase in bone marrow blasts from baseline value.
- >50% increase in circulating blasts from baseline value with absolute blast count $> 1000/\text{mm}^3$
- Development of biopsy-proven extramedullary disease, or new sites of extramedullary leukemia.

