13.2 Sample Size and Accrual

During the dose escalation phase, dose escalation will be conducted according to a standard 3+3 dose escalation schema, and approximately 18 response-evaluable patients will be enrolled. The MTD/RP2D cohort will have at least 6 patients.

The sample sizes for the Phase II study are estimated using a one-sided test at a significance level of $\alpha=0.1$ with power of 80%. To perform the phase 2 study, we will consider a Simon's stage 2 design (See Study Overview Diagram) (39, 40). The primary objective of the phase 2 portion of the study is to detect an efficacy signal that warrants further development of the combination in AML, which will likely be annotated by molecular genetic mutational subgroups. It is most likely those will exist within the rubric of Flt3 mutation. The primary measure of efficacy for the phase 2 portion will be ORR, which will include CR, CRp, CRI, and PR. Best response will be assessed by the end of Cycle 3 of TAK-659/Ixazomib combination for the purpose of an interim analysis between Stage 1 and Stage 2. The Flt3WT and Flt3mut cohorts will proceed to the second stage if patients respond by CR, CRp, CRI.

It has been established in other trials involving single-agent Flt3-selective inhibitor(s), such as FDA-approved Gilteritinib, that a composite complete response rate of approximately 40% occurs in AML patients with Flt3 mutations (41). **However, in cases of subclonal mutant Flt3 allele burden, this may not occur, especially because the epigenetic co-mutation driver is not addressed by the TKI.** In such cases, we will stratify response rates of Flt3 mutant cohorts by mutFlt3 Variant Allele Frequency (VAF) in order to address the possibility that the proteasome inhibitor Ixazomib may contribute to clonal reductions of the clones bearing epigenetic comutational driver allele as well as a subclonal mutFlt3 population, or those that lack the mutant Flt3 allele altogether. However, despite this advantage, we would not accept markedly inferior response rates overall should they indicate a response rate less than expected for active single agent Flt3 inhibitor, and therefore set the futility threshold below 30%.

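### Section 13.7.1 defines the primary ORR as CRs and PRs, which conflicts with the four-class ORR (CR, CRp, CRi, PR) in 2.2.1, 13.2 and the synopsis.

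*Combined protocol and SAP*

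**What the plan says.** The phase II primary endpoint is given in several places.

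- Section 2.2.1 (Primary Endpoint): "Overall response rate (ORR) defined as CR, CRp, CRi, and PR", by the International Working Group criteria.
- Section 13.2 (Sample Size and Accrual): "The primary measure of efficacy for the phase 2 portion will be ORR, which will include CR, CRp, CRI, and PR". The synopsis (Study Design and Statistical Considerations) names the same four classes.
- Section 13.7.1 (Primary Objective, phase II portion): "ORR is defined as the rate of CRs and PRs in the response-evaluable population". It is to be estimated with 95% exact binomial intervals that take the two-stage design into account.

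Sections 8.2 and 10 define the classes. CRi/CRp is a category of its own, for the case where "some patients fulfill all of the criteria for CR except for residual neutropenia" or thrombocytopenia. PR requires the haematologic values of a CR, with marrow blasts reduced by at least half to 5-25%.

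Section 13.2 also holds the decision rules. Wild-type: stop at 1 or fewer responses in 9, success at 5 or more in 16. Mutant: stop at 2 or fewer in 8, success at 8 or more in 20.

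**The concern.** Section 13.7 tells the statistician what to compute, and its definition of the primary numerator differs from the endpoint section. A CRp or CRi patient has no other class to fall into: the counts are too low for CR, and PR demands the same counts. On a literal reading, a patient with under 5% marrow blasts and incomplete platelet recovery is a non-responder. A patient with 20% blasts (down by at least half) and recovered counts is a responder.

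The direct consequence is that the reported primary ORR and its interval would be too low and would not estimate the 2.2.1 endpoint. A second consequence is conditional. If the 13.7.1 numerator were carried over to the cutoffs in 13.2, a regimen at the design alternative would be judged on a lower rate than the one those cutoffs were set for.

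**Working it through.** **Inputs.** From 13.2: wild-type p1 = 0.40, continue if more than 1 of 9, success if at least 5 of 16. Mutant p1 = 0.55, continue if more than 2 of 8, success if at least 8 of 20. Assumed: f, the share of true responses that are CRp or CRi. The documents give no value of f for the combination, so a range is shown.

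**Step 1: the designs as stated (f = 0).** With stage sizes n1 and n, stage 1 limit r1 and final cutoff c,

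P(success) = Σ over x from r1+1 to n1 of Bin(x; n1, p) × P[Bin(n − n1, p) ≥ c − x].

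- Wild-type at p = 0.40: 81.5%. A search over designs returns the plan's minimax design (1/9, 5/16) exactly.
- Mutant at p = 0.55 with the stated 8/20: 88.1%. Whether 8/20 meets the stated alpha is a separate question. The cutoff is used here as written.

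**Step 2: the reported rate under 13.7.1.** Counting only CR and PR, the expected rate is p1 × (1 − f).

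- f = 25%: 0.40 × 0.75 = 30.0% (wild-type); 0.55 × 0.75 = 41.3% (mutant).
- f = 1/3: 0.40 × 2/3 = 26.7%; 0.55 × 2/3 = 36.7%.
- f = 50%: 0.40 × 0.5 = 20.0%; 0.55 × 0.5 = 27.5%.

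This understatement needs no assumption about the cutoffs.

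**Step 3: the chance of success if that numerator is also used with the 13.2 cutoffs.** There are two variants.

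(a) CRp/CRi dropped at both looks: the Step 1 formula with p = p1(1 − f).

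(b) CRp/CRi dropped at the final look only: stage 1 counts all responses at rate p1; of x stage 1 responses, y ~ Bin(x, 1 − f) remain countable; stage 2 runs at p1(1 − f):

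P(success) = Σx Bin(x; n1, p1) Σy Bin(y; x, 1 − f) × P[Bin(n − n1, p1(1 − f)) ≥ c − y].

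| f | Wild-type (a) | Wild-type (b) | Mutant 8/20 (a) | Mutant 8/20 (b) |
|---|---|---|---|---|
| 0 | 81.5% | 81.5% | 88.1% | 88.1% |
| 25% | 52.9% | 54.4% | 54.1% | 60.6% |
| 1/3 | 41.2% | 42.6% | 38.6% | 44.8% |
| 50% | 19.1% | 20.1% | 12.7% | 15.5% |

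Variant (b) is closer to the text, because 13.2 names CRp and CRi for the stage 1 decision: "The Flt3WT and Flt3mut cohorts will proceed to the second stage if patients respond by CR, CRp, CRI". That sentence leaves out PR, which is a separate inconsistency. Variant (b) counts all four classes at stage 1.

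**Step 4: what the documents say about f.** Section 1.4.5 reports three responders in the single-agent AML study C34002: one CR and "2 CRs with incomplete hematologic recovery". That is 2 of 3, with an exact 95% interval of 9% to 99%. It does not fix f for this combination, dose and schedule.

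**The case against.** The strongest reply is that the word CRs in 13.7.1 is loose shorthand for the whole CR family. Section 1.4.5 uses it that way when it writes of "2 CRs with incomplete hematologic recovery", and 13.2 uses composite complete response for CR, CRi and CRp together. The endpoint section, the sample-size section and the synopsis all spell out four classes, and the benchmarks cited in 13.2 are largely composite-response rates. A deliberate change of endpoint is therefore unlikely, and a reader who infers one goes further than the documents do. What remains is that no section declares the shorthand. Where the protocol specifies what counts as an overall response it names the subclasses, and 13.7.1 is the one place that does not.

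A second reply is that 13.7.1 governs estimation, while the cutoffs sit in 13.2 under an explicit four-class definition. Section 13.2 also lets duration of response, time to progression, bridge to transplant and mortality inform the decision to expand. This stands. The losses in Step 3 arise only if someone carries the 13.7.1 numerator into the 13.2 rule. A reader might infer that an active regimen will be declared a failure, but the text does not make that follow.

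A reader might also infer from C34002 that most responders would be missed. Three single-agent patients, with the two CRi cases at 140 and 160 mg daily on continuous dosing, cannot carry that for a 100 mg, 15-of-21-day combination.

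**Conclusion.** The inconsistency is real and the sentence in 13.7.1 is wrong as written. Taken literally, it counts CRp and CRi patients as non-responders and understates the primary ORR and its interval by the factor (1 − f).

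If the same numerator were applied to the 13.2 cutoffs as stated, the chance of success at the design alternative would fall as follows, from 81.5% (wild-type) and 88.1% (mutant):

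- f = 25%: 53-54% and 54-61%
- f = 1/3: 41-43% and 39-45%
- f = 50%: 19-20% and 13-16%

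The lower end drops CRp/CRi at both looks and the upper end at the final look only. These figures rest on an assumed f and on that carry-over, and neither is established by the documents. The documents support a conflict over the primary numerator that has to be settled. They do not show an intended change of endpoint or that most responses would be lost. They also cannot show a departure from a registered endpoint, since no registry record is among them.

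**What to change.** Before phase II response data are reviewed, replace the ORR sentence in 13.7.1 with the 2.2.1 definition, for example: ORR is the proportion of the response-evaluable population whose best response is CR, CRp, CRi or PR. Let the term ORR in 13.7.2, and in the sentence of 13.8 that summarises ORR, refer to that definition. Leave the separate contrast in 13.8 of CR/CRp against PR/non-response as it is. It groups PR with non-response and is not an ORR definition.

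The cost is one sentence and two cross-references. The classes are already defined in 8.2 and 10, so no extra data or patients are needed. The timing matters because a numerator settled after responses are known would look data-driven.

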13.8 Exploratory Objectives and Pharmacokinetic Analysis

The data analyses for these exploratory objectives are mainly descriptive. We will begin such analyses by tabulating the pairwise combinations of class1/class2 mutations that occur within the Flt3- mutant vs. -wild type cohorts and summarize the frequency of these mutations (most frequent class 1 are Flt3mutation (both ITD and TKD) ~40%; vs. N/KRAS 20%); within class 2 (NPM1 40%, IDH2/IDH1 ~20%, TET2 ~15%, WT1 ~10%, ASXL1 15%). CR/CRp vs PR/nonresponse rates will be tabulated among groups based on presence of combinational number (combinational burden) and type, and will be compared by Fisher's exact test. ORR will be summarized with 95%CI and PFS will be analyzed by Kaplan-Meier methods in the whole study population and in the subgroups defined by the mutation subtypes. Additionally, we will explore the noted response groups based on identified markers from our prior trial that were predictive of ability to achieve or not remission, including ID1, JUN, HOXA, as well as the currently added markers- β -catenin and FOXM1, examining their individual association with remission status using logistic regression model.

The plasma concentrations of TAK-659 will be determined by validated liquid chromatography tandem mass spectrometry (LC/MS/MS) assay methods. The pharmacokinetic population will be those patients whom have at least one measurable post TAK-659 dose concentration. Plasma TAK-659 concentrations will be summarized by time postdose, grouped by dosing schedule, dose group, and dosing cycle and day. Mean and individual plasma TAK-659 concentration data will be plotted over time, grouped by dosing schedule, dose group, and dosing cycle and day.

Sparse Plasma PK data from Phase I and Phase II will be used for the estimation of PK parameters in the PK-Evaluable Population, as noted in the prior section. Dose proportionality of TAK-659 plasma exposures will be evaluated by visual inspection of plots of individual PK parameter values versus dose. If data permits, regression analysis using a power model will also be used to assess dose proportionality.

Plasma PK data from Phase I and Phase II may be used to explore the relationship between PD markers of SYK and FLT-3 inhibition (and their downstream targets) and TAK-659 exposure (as described in Biomarker Analysis) and may be used to explore the relationship between exposure and toxicity and exposure and effectiveness using graphical and/or pharmacostatistical approaches, as permitted by the data.

TAK-659 plasma concentration-time data collected in this study, together with data collected from other studies, may contribute to population PK analysis. If applicable, the specifics of the population PK modeling approaches will be described separately in a population PK analysis plan, and the results will be reported separately from the clinical study report.

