1.3 Acute Myeloid Leukemia Mutations

Poor outcomes are frequent among certain acute myeloid leukemias (AMLS) characterized by small numbers of cooperating mutations (1). In particular, this group represents the largest fraction of AMLs in young adults. The cooperating mutations commonly involve epigenetic mechanisms amenable to targeted interventions. Such targeted interventions may, collectively in combinations, but only rarely when given alone, reverse resistance both to single tyrosine kinase inhibitors (TKIs) (eg. Those for Flt3ITD) and to a range of chemotherapies (2). A notable example is the ability of proteasome inhibitor (PI), Bortezomib, to silence HoxA expression, which is a major resistance factor for AML (2).

Figure 1-1 (below). EZH2/PRC2 upregulation by PI

One of the earliest recognized, and most frequently occurring, driver mutations for AML is *Flt3ITD*. It does appear that prolonged maintenance administration of single TKIs may not be an optimal option for *Flt3ITD* AML as has proved to suffice for efficacy in chronic myeloid leukemia (CML).

[figure not shown]
Unlike the primacy of *BCR-ABL* mutation in the origins of CML, Flt3 tyrosine kinase oncogene mutations in AML arise late in the process of leukemogenesis and are most commonly preceded by mutations of epigenetic effectors such as *DNMT3A*, *ASXL1*, *TET2*, *IDH1/2*, *WT1* (3).

Mutations in these latter effectors, functioning at the level of chromatin and DNA, have a common end-function for promoting leukemic stem cell expansion, which involves master regulators from the *Hox-A* and *-B* alleles. Thus, a major attribute for *Flt3ITD* poor-risk AMLs is *HoxA/B* overexpression, and also expression of the TALE-factor collaborator *Meis1*, whose abundance distinguishes these AML subsets from those curable, but less frequent forms of AML with core-binding factor mutations (CBF+ve), which are largely devoid of *HoxA/B* and *Meis1*(4,5).

It is of crucial importance to emphasize the collaboration that occurs in essentially all cases of AML

bearing Flt3 mutations with one of the noted epigenetic modifiers (6).

Figure 1-2 (below). Virtually all Flt3 mutant AMLs have co-mutation of epigenetic effectors, affecting the Wnt pathway and HOXA locus

[figure not shown]

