Therefore, within the Simon's two-stage design, the Flt3 mutant cohort uses as null hypothesis of response rate $\leq 30\%$, versus an alternative hypothesis of response rate $\geq 55\%$. Based on a Simon 2-stage Optimal design, 8 patients will be accrued in the first stage. If there are 2 or fewer responses in the 8

patients, the study will be stopped. Otherwise, 12 additional patients will be accrued for a total of 20. The treatment will be recommended for further study if 8 or more responses are observed in 20 patients.

On the other hand, we will follow the above rationale that proteasome inhibitor Ixazomib may contribute specific targeting of the epigenetic co-mutation driver allele in order to enhance what has been a limited contribution to antileukemic efficacy of Flt3-selective TKI's, such as Gilteritinib, as observed within subclonal Flt3 mutant as well as Flt3wild-type disease cohorts (42; see de Boer B, et al. *Cancer Cell*.2018;34:674-689). Indeed, the phase I/II trial for Gilteritinib reported an 8% (average of 120mg and 200 mg dose cohorts) composite Complete Response rate (CRc), and an average 16% ORR for Flt3wild-type disease which was vastly inferior to Flt3 mutant (AE Perl, et al. *Lancet Oncology* 18: 1061, 2017 [ref 41][see Table S8]).

Thus, there is a great need to establish platforms to target the **epigenetic co-mutation drivers of the Wnt/β-catenin pathway to HoxA, such as TET2 and WT1, as well as DNMT3A, EZH2 and ASXL1, where our in vitro evidence obtained on mutationally annotated Flt3 wild-type disease demonstrates promising activity of the combination of TAK-659 and Ixazomib.** Indeed, Syk inhibition, not simply Flt3 inhibition by the dual Flt3/Syk inhibitor appears to play an important role in such settings. Further, we have evidence that not only does TAK-659's Syk inhibitory activity target resistance mechanisms in Flt3 mutant AML, but that in combination with Ixazomib, there exists unique efficacy within the Flt3 wild-type AML's arising from the above effectors.

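### The exploratory Fisher comparison of mutation-combination groups (13.8) is not stratified by FLT3 cohort, so a FLT3 difference in response can appear as an effect of mutation pairing

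*Combined protocol and SAP*

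**What the plan says.** Section 13.8 describes its exploratory analyses as mainly descriptive. It begins by "tabulating the pairwise combinations of class1/class2 mutations that occur within the Flt3- mutant vs. -wild type cohorts", which is a frequency count. The comparison of outcome follows. CR/CRp is set against PR/nonresponse in groups formed "based on presence of combinational number (combinational burden) and type, and will be compared by"; the method named is Fisher's exact test. That sentence gives no stratum, covariate, significance level or sidedness.

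Three other places bear on it:

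- Section 13.8 gives the class 1 frequencies: "most frequent class 1 are Flt3mutation (both ITD and TKD) ~40%; vs. N/KRAS 20" percent. FLT3 is thus both the cohort-defining marker and the commonest class 1 member of a pair.
- Section 1.3 states: "Virtually all Flt3 mutant AMLs have co-mutation of epigenetic effectors".
- Section 13.2 plans for different response by FLT3 status. The null rates are 30% (mutant) and 15% (wild type), and the alternatives are 55% and 40%. For an approved single-agent FLT3 inhibitor it cites a composite CR rate of about 40% in mutant disease and 8% in wild type, with an "ORR for Flt3wild-type disease which was vastly inferior to Flt3 mutant".

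The only FLT3-related stratification of response in Section 13 is by variant allele frequency inside the mutant cohort (13.2). That does not address this comparison.

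**The concern.** The scientific question is whether the number or type of cooperating class 1/class 2 mutations affects remission. If nearly all mutant patients are paired, a minority of wild-type patients are paired, and the cohorts respond differently, then paired and unpaired patients will differ in response even when pairing does nothing in either cohort. The null hypothesis of a pooled Fisher test is a single response rate across groups, so a FLT3 effect alone can make it false.

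What is at stake is interpretation. Section 2.2.3 lists the mutational complement that predicts response as an endpoint, Section 9 makes collaboration between FLT3 and epigenetic mutations a central hypothesis, and Section 13.9 looks for predictive biomarkers. A FLT3 difference reported as a pairing effect would feed into later patient selection.

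**Working it through.** **1. Sample sizes.** The synopsis gives 36 phase II patients, 16 wild type and 20 mutant. A Simon search at one-sided 0.10 and 80% power returns minimax n = 16 (9 in stage 1) for 15% versus 40%, and optimal n = 20 (8 in stage 1) for 30% versus 55%. The sizes reproduce. Only the sizes are used below; the response cut-offs do not enter.

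**2. Pair prevalence.** In mutants, virtually all is taken as 95%, which is 19 of 20. In wild type the protocol gives no figure, so it is built from the stated frequencies assuming independence:

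- Any class 2 mutation, using IDH1/2 20%, TET2 15%, WT1 10% and ASXL1 15%: 1 − 0.80 × 0.85 × 0.90 × 0.85 = 0.480. Adding one further 40% gene (NPM1 as in 13.8, or DNMT3A as in Section 9): 1 − 0.60 × 0.520 = 0.688.
- Class 1 by N/KRAS only: 20%, or 0.20/0.60 = 33% if all RAS mutations fall in wild-type disease. Pairing runs from 0.20 × 0.480 = 9.6% to 0.333 × 0.688 = 22.9%.
- NPM1 counted as class 1, as in Section 9: class 1 prevalence is 1 − 0.80 × 0.60 = 0.52 to 1 − 0.667 × 0.60 = 0.60. Pairing runs from 0.52 × 0.480 = 24.9% to 0.60 × 0.688 = 41.3%.

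The range is about 10% to 41%, or 1.5 to 6.6 of 16 patients.

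**3. How much of a FLT3 gap passes into the pairing contrast.** With 25% of wild type paired, the expected paired group is 19 mutant + 4 wild type = 23, and the unpaired group is 1 + 12 = 13. With no pairing effect, the apparent paired-minus-unpaired difference is the FLT3 gap × (19/23 − 1/13) = 0.749 × gap. A 15-point gap becomes 11 points, a 32-point gap 24 points and a 40-point gap 30 points. At 10% wild-type pairing the factor is 19/20.6 − 1/15.4 = 0.86. At 41% it is 19/25.56 − 1/10.44 = 0.65.

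**4. Rejection probability.** Let paired counts be Bin(20, 0.95) in mutants and Bin(16, q) in wild type, with responders binomial at the cohort rate whether paired or not. Sum the probabilities of all tables with two-sided Fisher p ≤ 0.05. For the stratified test, the number of paired responders in each cohort is hypergeometric given the cohort margins. The two distributions are convolved, and p is the sum of probabilities no larger than that observed.

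| Mutant vs wild-type response | Pooled, q = 10% | q = 25% | q = 41% | Stratified, range |
|---|---|---|---|---|
| 30% vs 15% (both null) | 8.6% | 5.9% | 3.6% | 1.0–1.5% |
| 55% vs 40% (both alternative) | 9.6% | 7.3% | 5.2% | 1.0–2.5% |
| 40% vs 8% (cited composite CR) | 37.5% | 25.3% | 14.0% | 0.8–0.9% |
| 55% vs 15% (mutant at alternative, wild type at null) | 52.7% | 37.8% | 22.7% | 1.0–1.4% |
| 40% vs 40% (no FLT3 effect) | 3.6% | 3.2% | 2.9% | 1.0–2.5% |

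The last row gives the reference: with no FLT3 effect the pooled test rejects about 3%.

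**5. Limiting case.** For a contrast that coincides with FLT3 status (20 vs 16), such as combination types containing FLT3 against the rest, the pooled test rejects 11.0%, 12.2%, 51.7% and 67.7% in the first four scenarios. No stratification can recover a pairing effect there.

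**6. Power of the stratified test.** Unpaired rates of 30%/15% or 25%/10% were used, with 13% to 41% of wild type paired. Power is about 9% to 15% for a true 25-point pairing effect and 21% to 38% for a 40-point effect.

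**The case against.** The best case for leaving the text alone has four parts.

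- **Exploratory status.** The analysis carries no significance level, and 13.7.1 disclaims any aim of showing that disease groups differ in outcome. This stands and limits the severity. It does not remove the problem, because the point estimate is distorted whether or not a p-value is read.
- **The large figures need a large FLT3 gap.** This also stands. At the plan's own 15-point gaps the pooled test rejects 4% to 10%. The 40% versus 8% rates belong to a different single agent, and 13.2 argues that this combination should work in wild-type disease. The 55% versus 15% scenario pairs one cohort's alternative with the other's null.
- **The planned grouping is by number and type, not paired versus unpaired.** A comparison of one pair with several could fall mostly within the mutant cohort. The table in the working is therefore a simplification, and confounding will vary by contrast.
- **The plan already looks within cohorts.** Section 13.8 counts pairs by cohort, and question 6 in Section 9 asks about pairing in wild-type disease. These show that a within-cohort comparison fits the intent, but neither stratifies the Fisher test.

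Two stronger readings are tempting. A reader might infer that pair status nearly coincides with FLT3 status, so that any rejection simply reflects FLT3. The documents support only one direction: mutants are nearly all paired. Sections 1.3 and 9 expect wild-type pairs through KRAS, NRAS, JAK2, CBL or NPM1. A reader might also infer that the single-marker models, "examining their individual association with remission status using logistic regression model", must carry FLT3 as a covariate. The protocol places HOXA downstream of FLT3, so adjustment asks a different question, namely association beyond FLT3. No size of distortion has been calculated for those models.

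**Conclusion.** The concern holds as a conditional one. As written, 13.8 allows a FLT3 difference in response to be read as an effect of mutation pairing, and nothing elsewhere in the plan stratifies that test. Roughly 65% to 86% of any FLT3 gap would pass into a paired/unpaired contrast. With no true pairing effect, the pooled test rejects about 4% to 10% at the design gaps, 14% to 38% at 40% versus 8%, and 23% to 53% at 55% versus 15%. The stratified test rejects about 1% to 2%.

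These figures rest on assumptions the documents do not fix: both cohorts reach full size, phase II patients only, 95% pairing in mutants, independent mutation frequencies in wild type, a binary grouping and a two-sided 5% level. The design rates are for ORR and the cited rates for composite CR, and neither is exactly the CR/CRp outcome being compared. The consequence is a possibly misleading mechanistic interpretation. The Simon decisions and the primary ORR analysis are unaffected.

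**What to change.** In 13.8:

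- State that response is compared across combination groups within each FLT3 cohort, and report within-cohort response rates with confidence intervals.
- Where a combined test is wanted, use an exact test stratified by FLT3 cohort (exact conditional Mantel-Haenszel).
- State that combination types containing FLT3 cannot be separated from FLT3 status in this trial.
- Optionally, show FLT3-adjusted versions of the marker logistic models as a sensitivity analysis beside the unadjusted ones, not in their place.

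The change is SAP wording only, since FLT3 status is required at entry and already defines the cohorts. The real cost is power: with about 1 unpaired patient among 20 mutants, that stratum contributes little, and the stratified test will seldom be significant. The report should say so, since it shows how little 36 patients can tell about pairing apart from FLT3.
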